5.1. Specific main objective

Extension of the central phenotypic and NGS genotypic characterization of the VWD in Spain, through the prospective recruitment in the Spanish VWD cohort of approximately 500 new patients with local historical VWD diagnosis (from approximately 38 centres)

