1.5. Correspondence to

[name] [name]

Chairman Servicio de Hematología.
Complexo Hospitalario Universitario A Coruña (Edificio Materno Infantil)
Servicio de Hematología y Hemoterapia
[name]
E mail: [contact]

2. Summary of grant request

The present Project is a third phase of the previous **PCM-EVW-ES** Project (*Batlle et al. Thromb & Haemost 2015*) with the aim of its extension, further analysis with an innovation development in the field of VWD based in the newer recently available methodologies. The aim of this project is to help the physician in a **more uniform characterization and therapy of VWD** in clinical practice, at an international level. **A reduction of the expenses in the diagnosis process** by using the new methodologies is pursued.

The **specific objectives** and corresponding **tasks** of the present project are as follows:

Main objective is:

1. Extension of the central phenotypic and NGS genotypic characterization of the VWD in Spain, through the prospective recruitment in the Spanish VWD cohort of approximately 500 new patients with local historical VWD diagnosis (from approximately 38 centres).

Secondary objective is:

1. Development of an electronic platform using this proposed algorithm. In a second step, some other mutation-oriented tests or investigations could be carried out for confirmation.

This project involves leading innovation and translational research with a direct impact on the quality of clinical care (applicability). To our knowledge there is no similar project in this field. Potential patents may derive from this project. It involves also development of e-learning and new information technologies (debate forum, ads, google search engine). This project may promote international collaboration. Development of an algorithmic platform that facilitates diagnosis and therapy orientation of VWD in clinical practice using the selected data from the overwhelming amount of information that new technologies, such as NGS, are producing.

3. State of art/study background

VWD overview in Spain

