The data obtained in that survey for diagnostic parameters indicated that the more widely used tests are FVIII activity (FVIII:C), VWF:RCo, and VWF:Ag, and, to a lesser extent, VWF:CB. The RIPA at low ristocetin concentration (that allow identified the type 2B), the plasma VWF capacity to bind exogenous FVIII (VWF:FVIIIB) (that can distinguish between hemophilia and type 2N VWD) and the multimeric analysis were test very little used due to their complexity. The limited use of these methods may lead to underdiagnosis of some patients. Also, the complexity, high cost, and experience required to perform a molecular study constitute the main reasons for that only five centers carried out this study by Sanger and the 50% of participants never request this study its low use. One of the conclusions of this the Spanish study was that because of the complexity and/or difficulty in performing some of the tests used in the diagnosis of VWD, supporting the centralization of these tests in laboratories that have the experience necessary to achieve a more uniform characterization.

The Molecular and Clinical Profile of von Willebrand Disease in Spain (PCM-EVW-ES) Project. Spanish Registry

Motivated by the success and experience of the European Project MCMDM-1VWD, a Spanish Registry on VWD has been initiated. Several European countries already have their own registry. In order to achieve a better comprehension of this complex pathology, it is necessary to rely on a patient database that must be as much extensive and detailed as possible [31].

A main feature of the PCM-EVW-ES is that the analysis of the samples has been centralized in three laboratories that have the experience necessary to achieve a more uniform characterization. It should be emphasized that this study was not intended as a prevalence study or as a quality assessment of the participant laboratories. The main goals of the study are:

- i. An assessment of the real diagnosis and therapeutic situation of VWD in Spain in normal clinical practice;
- ii. The achievement of a platform of recruited patients with the best possible characterization;
- iii. The development of a Spanish Working Group on VWD (recently created);
- iv. Participation in international projects on VWD (European Union VWD Group, Zimmerman Project, Type 3 VWD International "Registry Inhibitor Prospective Study (3WINTERS-IPS)";
- v. Elaboration of practical guidelines on diagnosis and therapy of VWD in Spain.

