 Dissemination of results: Target conferences to present the results of the project will be the 2017-19 meetings and congresses of ISTH, World Federation of Haemophilia, ASH, EAHAD, SETH, aside from partial results will be presented in other minor workshops or meetings. It is expected to publish some articles with the results of this project in international journals (e.g., Journal Thrombosis and Haemostasis, Blood, Haemostasis and Thrombosis, Haematologica, American

Journal of Haematology). The initial expected publications from the present Project are shown in **Annex VIII**

- 2. Ellaboration of a website similar to that carried out in the European project MCMDM-1VWD.
- 3. The partnership between LapiSoft and PCM workgroup has, among their aims, to participate and leading **innovation** and **research** projects with a **markedly translational** nature and with a direct impact on the quality of clinical care (**applicability**). To our knowledge there is no similar project in this field.
- 4. Potential patents may derive from this project.
- 5. Development of e-learning and new information technologies (forum discussion, ads, google search engine).
- 6. Eventually, there will be a study of all the data gathered, and will consult to experts on pattern recognition and **machine learning** in order to achieve more knowledge of the disease. New computer science algorithms will be defined, and the results of applying them, will be submitted for their publication in either medical or technical international journals.
- 7. We believe that this project will contribute to the clinical diagnosis of VWD at international level, especially in patients with particularly complex symptoms and diagnostic. This project is otherwise essential to establish international partnerships, participate in international studies and to access to additional funding resources.

Grant Baxalta

Molecular and clinical profile of VWD in Spain (pcm-evw.es)

Budget

March 31, 2016

13. Summary of the whole budget

CONCEPT	DESCRIPTION
Consumables	Central phenotipic study
	Central genotipic assay
Staff	Postdoctoral Investigator Fellowship
Services	Local patients sampling collection and transfer to central Laboratories
	Engineer Technical Teem budget contacted as a technical external service
Whole requested budget	US\$ 374,473.00

13.1. Postdoctoral Investigator Fellowship Research Medical Team.

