For the accomplishment of this project it is needed to contract a post-doctoral investigator (at half time) with a deep knowledge in VWF and VWD. His/her activity will include:

- 1. Central phenotipic analysis of the 500 samples.
- 2. Update of the database (monthly). Exhaustive bibliographical search will be realized as well as also there will be checked different database that already exist in order to incorporate all those mutations and polymorphisms that have been described recently, providing the most detailed information possible about them.
- 3. Analysis of controversy. To help to adopt a position in those cases in which exist controversy.
- 4. In collaboration with LapiSoft, will conduct some basic testing on each new feature developed and report any discrepancy with the initial specification.
- 5. Elaboration of reports and modifications according new requirements and features of the algorithm.
- 6. Validation of the platform.

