13.2. Sampling collection and transfer to central laboratories

This budget has been calculated estimating a recruitment of 400 patients from approximately 35 different centres from Spain with recollection of the samples from de local centres and transfer to Central Laboratory of La Coruña, Spain assuring to keep them permanently and adequately frozen. In order to make efficient this transfer, it will be carefully planned together with the enterprise chosen grouping as much as possible different centres form close geographical areas. Once received the samples, aliquot fractions will be sent to Central Laboratory of Barcelona for molecular analysis.

13.3. Engineer Technical Team (Lapisoft Projects S.L) contacted as a technical external service.

Based on Software engineer paradigms, Lapisoft will break down the implementation of the technical part of the project. These activities include the detailed design of the system by a System Analyst and a UX designer, the implementation by a software developer and the validation by a betatester. These will be considered for the full duration of the project:

- **Legal LOPD advising:** To assure the compliance of the Spanish data privacy law. Professional expert consulting will be required.
- **Cloud resources and support**: this includes the cost of the infrastructure plus the support plan for both systems.
- Machine learning consulting: As it was mentioned, since machine learning techniques will be applied to the dataset, external advising will provide guides to follow.

We wish to emphasized that the present project will be funded by the grant requested to Baxalta and it will not suppose additional costs to the FETH.

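### Planned recruitment is about 500 patients from about 38 centres in the main objective, but 400 from about 35 centres in the sample-transfer budget, with no explanation

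*Protocol*

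**What the plan says.** The size of the project is given in four places in the protocol.

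- **Section 2 (Summary of grant request), main objective:** "approximately 500 new patients with local historical VWD diagnosis (from approximately 38 centres").
- **Section 5.1 (Specific main objective):** the same target, "prospective recruitment in the Spanish VWD cohort of approximately 500 new patients with local historical VWD diagnosis (from approximately 38 centres").
- **Section 13.1 (postdoctoral fellowship), first duty:** "Central phenotipic analysis of the 500 samples".
- **Section 13.2 (sampling collection and transfer):** "This budget has been calculated estimating a recruitment of 400 patients from approximately 35 different centres from Spain".

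Section 13.2 also describes how samples travel. It provides for "recollection of the samples from de local centres and transfer to Central Laboratory of La Coruña", and then states: "Once received the samples, aliquot fractions will be sent to Central Laboratory of Barcelona for molecular analysis". The budget table in section 13 lists the corresponding line as "Local patients sampling collection and transfer to central Laboratories". No other part of the protocol describes how samples reach the central laboratories.

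**The concern.** The main objective has one numerical target, the number of new patients to be characterised centrally. Three statements put it at 500, and one describes a recruitment of 400. Sections 13.1 and 13.2 are adjacent items of one budget, yet they rest on different numbers.

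Section 13.2 does not present the 400 as part of a larger cohort, as the number expected to be evaluable, or as those left after losses. It calls it a recruitment. Two things are therefore unclear:

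- whether 400 recruited patients would be full delivery or a shortfall against the main objective;
- whether transport has been provided for all 500 samples that section 13.1 expects to be phenotyped.

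**Working it through.** **Can 500 be reproduced?** No. The protocol gives no precision target, power, effect size or loss rate from which 500 could be derived. It is a stated recruitment goal, so the check is a direct comparison of the stated figures, followed by a search for something that links them.

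**Inputs**

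| Source (Protocol) | Patients or samples | Centres |
|---|---|---|
| Sections 2 and 5.1 | about 500 | about 38 |
| Section 13.1 | 500 samples | not given |
| Section 13.2 | 400 | about 35 |
| Section 3.1, earlier phase | 556 analysed, 480 confirmed | not used |

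**Size of the gap**

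- Patients: 500 − 400 = 100, and 100/500 = 20%.
- Centres: 38 − 35 = 3, and 3/38 = 7.9%.
- Seen from 13.2: 500/400 = 1.25, so the full target is 25% more patients than that budget line assumes.

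The target of 500 and both centre counts are marked as approximate. The 400 is not, and a 20% difference is more than that word can cover.

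**Possible links between the two figures**

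1. *Fewer centres at the same yield.* The target implies 500/38 = 13.16 patients per centre. Then 35 × 13.16 ≈ 461, not 400. Section 13.2 itself implies 400/35 = 11.4 per centre.
2. *Only confirmed cases counted.* The earlier phase confirmed 480/556 = 86.3%. Applied to 500, this gives 500 × 480/556 ≈ 432, not 400.
3. *Losses.* A 20% loss would fit exactly, since 400/(1 − 0.20) = 500. No loss rate is stated, and the 400 is called a recruitment rather than a number remaining.
4. *Three centres exempt from transfer.* These would have to supply the missing 100, or 100/3 ≈ 33 patients each, about 2.9 times the 11.4 per centre elsewhere. This is arithmetically possible, but the protocol does not state it.

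**Effect on precision.** The 95% half-width is 1.96 × √(p(1 − p)/n). As illustrations, p is taken from the percentages reported for the earlier phase in section 3.1, and patients are treated as independent.

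| p | n = 500 | n = 400 |
|---|---|---|
| 96.5% (phenotype–genotype association) | 1.6 points | 1.8 points |
| 42.3% (local–central discrepancy) | 4.3 points | 4.8 points |

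The estimates would be almost as precise at 400 as at 500.

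**The case against.** The strongest reply is that the study size is not in doubt. It is stated as a target twice in the same words, and the phenotyping workload agrees with it. The 400 occurs once, as the costing basis of a line for collecting and shipping samples. A reader judging delivery would go to the objective.

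There is also a benign explanation that fits. The centre gap is exactly three. The protocol describes three medical teams, and of the earlier phase it says "the analysis of the samples has been centralized in three laboratories". Section 9 describes both the Catalan and the Valencia units as among the largest in Spain, so an above-average yield of about 33 patients each is plausible. It also weakens the equal-yield calculation above. If those hospitals were left out of a line for shipping from local centres, 35 centres and 400 patients could follow. Finally, the budget table shows no amount per item, so the absence of a fuller costing proves little.

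Part of this stands. The 400 is a budget assumption rather than a second statement of the objective, and no underfunding can be inferred.

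The benign explanation, however, is inference. Section 13.2 speaks of recruitment, not of a subset to be shipped. It sends samples to A Coruña first and only then forwards aliquots to Barcelona. On that route, patients of the Barcelona and Valencia units would still need transport to A Coruña, and only A Coruña's own patients clearly would not. Even if the explanation is right, the protocol needs a sentence saying so.

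**Conclusion.** The inconsistency is real and should be fixed. Sections 2, 5.1 and 13.1 rest on 500 patients or samples, with about 38 centres in sections 2 and 5.1. Section 13.2 rests on 400 patients and about 35 centres. The difference is 100 patients (20% of the target) and 3 centres, and it is not explained.

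The weight is minor to moderate. No bias or calculation error is shown, no test or precision target depends on the 500, and no shortfall of money is demonstrated. What is at stake is whether the main objective can be judged as met, and whether the only described sample route covers every patient it needs to cover.

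The comparison uses the stated figures alone, without any assumption on yield per centre. The document does not settle which figure is intended, although three of the four statements favour 500.

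**What to change.** Bring sections 2, 5.1, 13.1 and 13.2 to one number of patients and one number of centres.

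- **If 500 stands and all samples must travel:** change the basis in 13.2 to 500 patients and about 38 centres, and recalculate the transfer estimate. The number of patients behind it rises by 25%. The cost need not rise in proportion, because transfers are to be grouped by area, and it cannot be computed from the protocol because no amount per item is shown.
- **If 500 stands and some samples need no costed transfer:** add one sentence to 13.2 saying which 100 patients and which centres are exempt, and why, consistent with the route through A Coruña.
- **If 400 is the realistic recruitment:** restate sections 2, 5.1 and 13.1 as about 400 and align the centre count.

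The second and third options are wording only, from one sentence to edits in a few places. Only the first requires recosting.

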5.2. Secondary objective

Development of an electronic platform using this proposed algorithm. In a second step, some other mutation-oriented tests or investigations could be carried out for confirmation.

Overwhelming information provided from VWD phenotypical and genetic data requires the help of electronic applications.

6. Limitations of the study

i. A higher number of cases for simulation than that available at this moment desirable ▶ the future inclusion of newer cases will facilitate the platform improvement.

- ii. Existence of some complex cases that fail in the algorithm process (such as complex genetic changes) ▶ they are not frequent and, again, with their better knowledge will help to improve and refine the platform.
- iii. Potential legal problems with the corresponding foreign LOPDs in regard to the possibility of collaborative platform use ▶ an authorization from each particular country should be obtained by the collaborator research team in its country.
- iv. Nomenclature of the mutations and diagnostic assignment not always uniformly followed according the international standards and recommendations (for instance from ISTH-SSC VWF) the present project includes a regular revision of the international information and the adaptation in case of controversy or non-uniform report.
- v. The utility of the machine learning approach will require the future participation of cohorts of patients from other countries to achieve solid information in regard to the meaning of some VWF genetic variations.

7. Expected achievements

- I. To improve the database for the Spanish Registry on VWD to save the already available data from the records of PCM-VWD-ES project, that allows interconnection with newer future electronic applications, facilitating further studies.
- II. Enlargement of the Spanish VWD patients cohort uniformly well characterized at the phenotypic and genetic levels. Future incorporation of new patients potentiating the development of this registry.
- III. Achievement of a platform maintainable, potentially scalable, extensible, usable in clinical practice, validated and accepted at an international level that allows a more accurate and uniform diagnosis and therapy of the VWD patients.
- IV. Potential ISTH acceptance of this platform to be used internationally.

8. References

- **1**. Lillicrap D. von Willebrand disease: advances in pathogenetic understanding, diagnosis, and therapy. Hematology 2013; 254-60.

They have a broad expertise in clinical diagnosis and therapy of patients with VWD since the unit is the Congenital Coagulopathies Comprehensive Care Centre in Catalonia and is one of the largest in Spain, taking care of more that and none thousand patients and relatives. The Hemophilia Unit has an experienced multidisciplinary team comprised for a total of 12 professionals who perform their work exclusively on this service, developing comprehensive care of the patients and relatives. The continuous monitoring of the quality of care through clinical sessions, has converted the unit into a worldwide reference center for the congenital coagulation disorders. Equally significant, is the participation of the Unit in multicenter international clinical trials, as well as in phase III & IV trials for new drugs. Hemophilia Unit has the human and material resources necessary for diagnosis, patient selection and sample extraction. Specific coagulation studies are performed routinely in the Coagulation Laboratory of the Hospital Universitari Vall d'Hebron.

This Unit has a dual character since their foundation in 1998: diagnostic support in congenital coagulation disorders as well as other hereditary diseases; research and development of new approaches in the field of medical diagnostics and therapeutics. In-depth studies of molecular events present in some affected individuals and the relation genotype-phenotype constitute the most basic area of the team objectives. The UDTM is comprised of a talented staff of scientists with a broad range of expertise to support clinical needs. Among the primary tasks of the lab there is the applied research in the molecular diagnosis of congenital blood coagulation disorders, genetic counseling and prenatal diagnosis. Also, an important part of the current research objectives is the innovation in technological tools and their transfer to the routine laboratory. The protocols designed and optimized in our laboratory for the molecular diagnosis of HA (Vidal et al. 2001. Thromb Haemost 85: 580-3) and HB (Vidal et al. 2000. Br J Haematol 111: 549-51) that are currently used to provide routine care service (certified according to the ISO 9001 standard), includes identification of the molecular defect in patients and offered genetic counseling and prenatal diagnosis. Also, the developed technology has been transferred to other national centers involved in diagnosis of hemophilia. These protocols were recognized as an outstanding technological contribution among international experts in the field. The UDTM counts with a molecular biology laboratory with three fullequipped independent work areas: pre-PCR, post-PCR and cell culture.

 Dissemination of results: Target conferences to present the results of the project will be the 2017-19 meetings and congresses of ISTH, World Federation of Haemophilia, ASH, EAHAD, SETH, aside from partial results will be presented in other minor workshops or meetings. It is expected to publish some articles with the results of this project in international journals (e.g., Journal Thrombosis and Haemostasis, Blood, Haemostasis and Thrombosis, Haematologica, American

Journal of Haematology). The initial expected publications from the present Project are shown in **Annex VIII**

- 2. Ellaboration of a website similar to that carried out in the European project MCMDM-1VWD.
- 3. The partnership between LapiSoft and PCM workgroup has, among their aims, to participate and leading **innovation** and **research** projects with a **markedly translational** nature and with a direct impact on the quality of clinical care (**applicability**). To our knowledge there is no similar project in this field.
- 4. Potential patents may derive from this project.
- 5. Development of e-learning and new information technologies (forum discussion, ads, google search engine).
- 6. Eventually, there will be a study of all the data gathered, and will consult to experts on pattern recognition and **machine learning** in order to achieve more knowledge of the disease. New computer science algorithms will be defined, and the results of applying them, will be submitted for their publication in either medical or technical international journals.
- 7. We believe that this project will contribute to the clinical diagnosis of VWD at international level, especially in patients with particularly complex symptoms and diagnostic. This project is otherwise essential to establish international partnerships, participate in international studies and to access to additional funding resources.

Grant Baxalta

Molecular and clinical profile of VWD in Spain (pcm-evw.es)

Budget

March 31, 2016

13. Summary of the whole budget

CONCEPT	DESCRIPTION
Consumables	Central phenotipic study
	Central genotipic assay
Staff	Postdoctoral Investigator Fellowship
Services	Local patients sampling collection and transfer to central Laboratories
	Engineer Technical Teem budget contacted as a technical external service
Whole requested budget	US\$ 374,473.00

13.1. Postdoctoral Investigator Fellowship Research Medical Team.

For the accomplishment of this project it is needed to contract a post-doctoral investigator (at half time) with a deep knowledge in VWF and VWD. His/her activity will include:

- 1. Central phenotipic analysis of the 500 samples.
- 2. Update of the database (monthly). Exhaustive bibliographical search will be realized as well as also there will be checked different database that already exist in order to incorporate all those mutations and polymorphisms that have been described recently, providing the most detailed information possible about them.
- 3. Analysis of controversy. To help to adopt a position in those cases in which exist controversy.
- 4. In collaboration with LapiSoft, will conduct some basic testing on each new feature developed and report any discrepancy with the initial specification.
- 5. Elaboration of reports and modifications according new requirements and features of the algorithm.
- 6. Validation of the platform.

